
Study Size:
	
In Version 3.0 of this protocol, approximately 1600 patients across approximately 160 participating sites in the United States (US), European Union (EU), Australia, and sites participating in Study 105MS302 and 105MS303 in other countries were planned to be enrolled. In January 2017, following a decision by Biogen to limit enrollment to approximately 1100 patients, a Protocol Clarification Letter was sent to all study sites providing official notification that enrollment into the study should be stopped. The current target sample size is expected to provide acceptable precision around the estimates of the proportion of patients experiencing SAEs and ensure a reasonable likelihood of observing rare AEs over a 5-year period. The target sample size will also provide acceptable precision around the overall effectiveness endpoint of the proportion of patients with no evidence of disease activity clinically (cNEDA), which is defined as having no relapses and no disability progression.

Data Analysis:
	
Statistical analyses will be based on all patients who enroll in the study and receive at least one within-study dose of Plegridy. Analyses will be conducted separately for patients newly-prescribed Plegridy (Plegridy-naïve) from those who have previous exposure to Plegridy prior to study enrollment (Plegridy-experienced). Statistical analyses will generally be descriptive and exploratory in nature. No formal statistical hypothesis testing is planned.
 
Ninety-five percent confidence intervals (95% CIs) for the incidence and incidence rate point estimates will be calculated using the negative binomial distribution and the Poisson distribution, respectively. Analyses of continuous endpoints may include summaries of values over time, change from baseline over time, shift tables, and/or summaries of worst post-baseline values.
 
The proportion of patients with cNEDA will be calculated over time (e.g., Baseline to Year 1, Baseline to Year 2, etc.) as well as

CONFIDENTIAL

The information contained herein may not be used, disclosed, or published without the written consent of Biogen MA Inc.

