Eligible patients may be naïve to Plegridy at the time of enrollment, but need not be naïve to other MS treatments, and must not currently be enrolled in any other clinical trial of an investigational product, unless according to the study Medical Director it does not conflict with the observational study (e.g., health economic studies). Patients with previous exposure to Plegridy will be evaluated separately from patients who are newly prescribed Plegridy because prevalent Plegridy-users may be more or less likely to experience AEs, may fail to report AEs that occurred before study enrollment, or may have discontinued Plegridy treatment due to an AE. Patients participating in other clinical studies are excluded so as not to unduly confound causality assessments when the safety profile of a concomitant experiment agent has yet to be established and/or the physician is blinded to the patient's treatment assignment.

The decision to enroll a patient in this study must not be made until after the Prescribing Physician and patient decide to begin Plegridy treatment and Plegridy treatment has been prescribed. Patients (or their legally authorized representative) agreeing to participate in the study will read and sign the informed consent and confidentiality statements. Enrollment data will be collected by the Prescribing Physician at the routine clinical visit at which Plegridy is first prescribed. For patients with previous exposure to Plegridy prior to enrollment, data will be collected from the time of first dose of Plegridy through enrollment in this or previous studies (see Section 8.3.1 for details). During enrollment, the Prescribing Physician will also inform female patients of childbearing potential if a pregnancy registry is being conducted independently of this observational study.

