8.6.3. Demography and Baseline Disease Characteristics

Demographic and baseline disease characteristics will be summarized overall. The demographic profile (age, sex, and race [where legally allowed]), relevant medical history, MS disease history, MS treatment prior to start of Plegridy, and concomitant medications and therapies used will be listed and summarized using appropriate descriptive statistics for categorical and continuous variables. Categorical variables will be summarized using frequencies and percentages. Continuous variables will be summarized using mean, SD, median, and maximum and minimum values. Two-sided

CONFIDENTIAL

The information contained herein may not be used, disclosed, or published without the written consent of Biogen MA Inc.

95% CIs will be used. In general, categorical data will be summarized using frequency and percentage, and continuous variables will be summarized using descriptive statistics (number, mean, SD, median, minimum, and maximum). For continuous variables, if the data are approximately normally distributed, then a 95% CI for the mean change will be calculated. If the data are not normally distributed, then the interquartile range will be presented with the median. All analyses will be conducted using a two-sided test and a significance level of 0.05. Due to the inherent differences in Plegridy-naïve patients and those who had exposure to Plegridy prior to study enrollment, analyses will be conducted separately for these two groups. The definition of Plegridy-naïve will be described in the SAP.

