8.6.7. Sample Size Considerations

While no formal statistical hypotheses are being tested in this descriptive observational study, 1100 patients newly or currently prescribed with Plegridy are being targeted for enrollment. All patients will be followed for up to five years, and follow-up is planned regardless of whether patients discontinue treatment with Plegridy. Because this is a long-term observational program, a sample size of 1100 patients was chosen to ensure a reasonable likelihood of observing rare AE events over a 5-year period and to provide informative CIs for SAE incidence and incidence rate point estimates. Based on the withdrawal/discontinuation rates observed in the Plegridy Phase III clinical trial (Study

CONFIDENTIAL

The information contained herein may not be used, disclosed, or published without the written consent of Biogen MA Inc.

105MS301, 1-year) and prior Biogen observational studies, it is expected that approximately 3520–3960 person-years of follow-up will accrue.

With a sample size of 1100 patients, the probability of observing an event with an incidence rate of 0.10% (1/1000 persons) will be approximately 67%; the probability of observing an event with an incidence rate of 0.09% (90/100,000 persons, or 1/1111 persons) will be approximately 63%; the probability of observing an event with an incidence rate of 0.08% (80/100,000 persons, or 1/1250 persons) will be approximately 59%; and the probability of observing an event with an incidence rate of 0.054% (54/100,000 persons, or 1/1851 persons) will be approximately 48%.

For the co-primary endpoint of cNEDA, assuming a dropout rate up to 20%, a sample size of 1100 patients, and an expected 68.4% of patients free from clinical disease activity at the end of one year (Study 105MS301, 1-year), a two-sided 95% CI for the observed proportion of patients free from measured clinical disease activity at the end of one year using large sample normal approximation will extend 0.027 to 0.031 from the observed proportion for an expected proportion of 0.684.

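### The cNEDA half-width of 0.027 to 0.031 in 8.6.7 holds only for both cohorts pooled, while the protocol calls for separate analyses and gives no precision for either cohort

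*Protocol*

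**What the plan says.** Section 8.6.7 sets one target for both kinds of patient: "1100 patients newly or currently prescribed with Plegridy are being targeted for enrollment". For cNEDA it allows for dropout of 0% to 20%, takes "an expected 68.4% of patients free from clinical disease activity at the end of one year" from the one-year pivotal trial, and concludes that "a two-sided 95% CI for the observed proportion", by the normal approximation, "will extend 0.027 to 0.031 from the observed proportion for an expected proportion of 0.684". The Study Size entry of the abstract relies on this: "The target sample size will also provide acceptable precision around the overall effectiveness endpoint".

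On how the data will be analysed, section 8.6.3 points to inherent differences between Plegridy-naive and previously exposed patients and says that "analyses will be conducted separately for these two groups". The Data Analysis entry of the abstract says the same of the statistical analyses in general. Section 8.2.4.1 adds: "Patients with previous exposure to Plegridy will be evaluated separately from patients who are newly prescribed Plegridy". Section 8.6.4.1 repeats the separation for safety.

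The protocol gives neither the expected nor the actual number of patients in each cohort, and no precision for either.

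**The concern.** The precision statement and the planned analysis refer to different sets of patients. If the cNEDA results are reported by cohort, as the abstract and 8.6.3 indicate, each interval rests on only part of the 1100 patients. At least one of the two intervals must then be clearly wider than the figure in 8.6.7. That figure is the only numerical precision given for a co-primary endpoint, and the abstract repeats its conclusion as support for the sample size. A reader who takes 0.027 to 0.031 as the expected width of the reported cohort results would be misled, most of all for the smaller cohort.

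**Working it through.** **Inputs, all from 8.6.7:** N = 1100 (both cohorts together), dropout 0% to 20%, expected proportion p = 0.684, two-sided 95% (z = 1.96), normal approximation. The split between naive and experienced patients is not stated, so it is varied below. The same p and the same dropout are assumed in each cohort.

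**Formula:** half-width = 1.96 × √(p(1 − p)/n), with p(1 − p) = 0.684 × 0.316 = 0.2161.

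**Step 1, reproduce the printed range**
- n = 1100: 1.96 × √(0.2161/1100) = 0.0275
- n = 1100 × 0.8 = 880: 1.96 × √(0.2161/880) = 0.0307

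To three decimals these are the printed 0.027 (0.02747 before rounding) and 0.031. The range is therefore the pooled study at no dropout and at 20% dropout.

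**Step 2, half-width by cohort (first value no dropout, second value 20% dropout)**

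| Assumed split | Larger cohort | Half-width | Smaller cohort | Half-width |
|---|---|---|---|---|
| 50:50 | 550 | 0.039 to 0.043 | 550 | 0.039 to 0.043 |
| 70:30 | 770 | 0.033 to 0.037 | 330 | 0.050 to 0.056 |
| 80:20 | 880 | 0.031 to 0.034 | 220 | 0.061 to 0.069 |
| 90:10 | 990 | 0.029 to 0.032 | 110 | 0.087 to 0.097 |

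**Step 3, a bound that does not need the split.** The smaller of two cohorts cannot exceed 1100/2 = 550. Its half-width is therefore at least 1.96 × √(0.2161/550) = 0.0389 with no dropout, and at least 1.96 × √(0.2161/440) = 0.0434 with 20% dropout. Both exceed 0.031, so no split puts both cohorts inside the printed range.

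**Step 4, how large one cohort must be to round to 0.031.** The half-width must be below 0.0315, so n must be at least (1.96/0.0315)² × 0.2161 ≈ 837 evaluable patients. That is 837/1100 = 76% of all patients with no dropout. With 20% dropout it needs 837/0.8 ≈ 1046 enrolled, or 95% of all patients.

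**The case against.** The strongest reply is that nothing is miscalculated. Section 8.6.7 states its basis (1100 patients newly or currently prescribed, Year 1, up to 20% dropout), and the range follows exactly. This stands: the issue is a mismatch with the planned analysis and not an arithmetic error.

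Secondly, a pooled cNEDA estimate may well be produced. Section 8.6.5.1 defines a single effectiveness population, 8.6.5.3 describes the cNEDA analysis without mentioning cohorts, and 8.6.5.2 foresees proportions of the total study population as well as by subgroup. The reason given in 8.2.4.1 for separating the groups concerns adverse events only. The printed range would apply to such a pooled estimate. This also stands, but it does not settle the matter. The abstract and 8.6.3 call for separate analyses without restricting this to safety, and 8.6.7 gives no precision for them.

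Thirdly, a reader might infer that neither cohort can reach the stated width. The document does not support that. The split is unknown, and a dominant cohort could reach it: 880 patients with no dropout give 0.031. Only the smaller cohort must be wider.

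Finally, the study is descriptive with no formal hypotheses, enrollment has ended, and 8.6.7 ties the choice of 1100 mainly to rare adverse events and serious adverse event intervals. Acceptable precision has no numerical threshold, so no commitment is breached. This limits the consequence but leaves the precision statement incomplete for the analysis planned.

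**Conclusion.** The point holds in limited form. The range 0.027 to 0.031 is correct for the pooled study at Year 1, but it does not describe the separate cohort estimates that the abstract and 8.6.3 call for. Under any split the smaller cohort has a half-width of at least 0.039 (0.043 with 20% dropout). At an equal split both cohorts are about 41% wider than the pooled figure (√2 = 1.41). The bound rests on the protocol's p = 0.684 applying in each cohort. The split-specific values are illustrations because the protocol gives no split.

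A reader might also fault 8.6.7 for giving no Year 5 precision when the objective is long-term effectiveness. That is not an error. The section claims only Year 1 precision, and a Year 5 figure would need a later cNEDA proportion and a retention pattern that the protocol does not supply.

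**What to change.** In 8.6.7, and in the Study Size entry of the abstract where it relies on this precision:
- Label 0.027 to 0.031 as the pooled Year 1 half-width.
- State the actual numbers of Plegridy-naive and Plegridy-experienced patients. Section 8.1 says that enrollment ended in January 2017, so these should be available.
- Give the expected Year 1 half-width for each cohort from those numbers, over the same 0% to 20% dropout.

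Precision for later years may be added as an illustration, with its assumed proportion and retention stated, but this is optional.

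The cost is a recalculation and about one paragraph of text, with no added patients. The downside is that the stated precision becomes less favourable, particularly for the smaller cohort.

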8.7. Quality Control

A study monitoring plan, including for-cause monitoring, that is appropriate for the study design will be developed and implemented.

8.7.1. Study Site Initiation

The Prescribing Physician must not enroll any patients in this study prior to completion of a study initiation visit, conducted by Biogen or designee. During the site initiation visit, the monitor will provide training on the protocol and conduct of the study to the Prescribing Physician and all site staff involved in the study.

8.7.2. Quality Assurance

During and/or after completion of the study, quality assurance officers named by Biogen or the regulatory authorities may wish to perform onsite audits. The Prescribing Physician will be expected to cooperate with any audit and to provide assistance and documentation (including source data) as requested.

8.7.3. Monitoring of the Study

In order to ensure the integrity of the data, sites will be monitored. Site monitoring will be performed by IQVIA clinical research associates to examine compliance with the protocol and adherence to the data collection procedures, to assess the accuracy and completeness of submitted clinical data, and to verify that records and documents are being properly maintained for the duration of the study. The monitor will perform source data verification by review of original patient records.

The monitor will close out each site remotely after the last patient's final follow-up assessment is completed, all data have been entered and all outstanding monitoring issues have been resolved or addressed. All monitoring procedures and frequency of monitoring

CONFIDENTIAL

The information contained herein may not be used, disclosed, or published without the written consent of Biogen MA Inc.

visits will be described in a Monitoring Plan. Monitor contact details for each participating site will be maintained in the Investigator Site File.

Biogen or its designee representatives and competent regulatory authorities may conduct onsite visits at the study facilities for the purpose of monitoring various aspects of the study, including all study-related documents and other materials at the site, including the Investigator Site File, the completed eCRFs and the patients' original medical records. Audits may be conducted at any time during or after the study to ensure the validity and integrity of the study data. The Prescribing Physician must agree to Biogen-authorized personnel having direct access to patient (or associated) files for the purpose of verifying entries made in the eCRF, and assist with their activities, if requested. Adequate space and time for monitoring visits should be made available by the Prescribing Physician or study staff. The site must complete the eCRFs in a timely manner and on an ongoing basis to allow regular review by the study team.

8.7.4. Retention of Study Data

The minimum retention time for study records will meet the strictest standard applicable to that site, as dictated by any institutional requirements or local laws or regulations. Prior to proceeding with destruction of records, the Prescribing Physician must notify Biogen in writing and receive written authorization from Biogen to destroy study records. In addition, the Prescribing Physician must notify Biogen of any changes in the archival arrangements including, but not limited to, archiving at an off-site facility or transfer of ownership if the Prescribing Physician leaves the site.

8.8. Limitations of the Research Methods

Additional confounders may not be fully captured in an observational study due to limitation of resources. Patient-reported outcomes are subject to information bias such as recall bias. Sites with smaller numbers of patients enrolled have fewer AE events reported, leading to seemingly decreased AE rates.

8.9. Other Aspects

8.9.1. Study Funding

Biogen is the Sponsor of the study and is funding the study. All financial details are provided in the separate contract(s) between the institution, Prescribing Physician, and Biogen.

8.9.2. Publications

Details are included in the clinical trial agreement for this study.

Any publication of the results from this study must be consistent with Biogen's publication policy and guided by the Uniform Requirements for Manuscripts Submitted to Biomedical Journals: Writing and Editing for Biomedical Publication of the International Committee of Medical Journal Editors, updated April 2010 [International Committee of Medical Journal Editors 2010]. The rights of the Investigator and of

CONFIDENTIAL

The information contained herein may not be used, disclosed, or published without the written consent of Biogen MA Inc.

Biogen with regard to publication of the results of this study/registry are described in the Investigator contract.

All reporting will be consistent with the STROBE (STrengthening the Reporting of OBServational studies in Epidemiology) Initiative checklist for cohort studies [von Elm 2008].

CONFIDENTIAL

The information contained herein may not be used, disclosed, or published without the written consent of Biogen MA Inc.

9. PROTECTION OF HUMAN SUBJECTS

Biogen and the participating physicians must comply with this protocol and applicable International Conference on Harmonisation (ICH), Good Clinical Practices (GCP), and Good Pharmacovigilance Practices (GVP) guidelines and conduct the study according to local regulations. The patient's privacy; physical, mental, and social integrity; and the confidentiality of his or her personal information will be strictly respected in accordance with the World Medical Association Declaration of Helsinki.

The study will be conducted in compliance with the US Food and Drug Administration Title 21 Code of Federal Regulations Part 50 – Protection of Human Patients and/or Part 56 – Institutional Review Boards (IRBs); the ICH Good Clinical Practice guidelines (May 9, 1997) as they apply to postmarketing observational studies; the Declaration of Helsinki and its amendments; and the Health Insurance Portability and Accountability Act of 1996.

9.1. Institutional Review Board and Independent Ethics Committee

Participating physicians must obtain IRB or independent ethics committee (IEC) approval or favorable opinion, respectively, of the protocol, ICF, and other required study documents prior to starting the study, as required per local regulations. Patient enrollment will not start before Biogen has obtained written confirmation of an approval or favorable opinion from the relevant central or local IRB or IEC, as required per local regulations.

If the Prescribing Physician makes any changes to the ICF, Biogen must approve the changes before the ICF is submitted to the ethics committee. A copy of the approved ICF must be provided to Biogen. After approval, the ICF must not be altered without the agreement of the relevant ethics committee and Biogen. Before implementation of any substantial changes to the protocol, protocol amendments will also be submitted to the relevant IRB/IEC in a manner consistent with local regulations. Pertinent safety information will be submitted to the relevant IECs during the course of the study in accordance with local regulations and requirements.

It is the responsibility of the Prescribing Physician to ensure that all aspects of institutional review are conducted in accordance with current governmental regulations. It is the responsibility of the Prescribing Physician to have prospective approval of the study protocol, protocol amendments, and ICFs, and other relevant documents, if applicable, from their local IRB/IEC and provide documentation of approval to the CRO. All correspondence should be retained in the Investigator File.

Biogen must receive a letter documenting ethics committee approval, which specifically identifies the protocol, protocol number, and ICF, prior to the initiation of the study. Protocol amendments will be subject to the same requirements as the original protocol.

A progress report must be submitted to the ethics committee at required intervals and not less than annually.

At the completion or termination of the study, the investigational site must submit a close-out letter to the ethics committee and Biogen. Should the study be terminated for

CONFIDENTIAL

The information contained herein may not be used, disclosed, or published without the written consent of
Biogen MA Inc.

any unanticipated reason, the Prescribing Physician will be responsible for informing the IRB/IEC of the early termination.

9.2. Subject Information and Consent

Prior to any data collection under this protocol, written informed consent with the approved ICF must be obtained from the patient or patient's legally authorized representative, as applicable, in accordance with local practice and regulations. Written informed consent must be obtained from all patients participating in a clinical study conducted by Biogen.

Information about the study and the voluntary nature of participation must be explained to the patient, if applicable. The patient must be given sufficient time to consider whether to participate in the study. A copy of the ICF, signed and dated by the patient, must be given to the patient. Confirmation of a patient's informed consent must also be documented in the patient's study file prior to any data collection under this protocol.

Each ICF should contain an authorization allowing the Prescribing Physician and Biogen to use and disclose PHI in compliance with local law.

The signed ICF will be retained with the study records.

Written informed consent must be obtained from patients who participated in Study 105MS302 or Study 105MS303 to link their data collected from Study 105MS302 and Study 105MS303, respectively, with the data for this study by unique identifier.

